- continuously and systematically collect, evaluate, and archive relevant demographic and clinical information on patients belonging to chronic pain treatment centers, making it available for studies and research.
- promote the use of uniform and comparable classification systems, definitions, and records in the structures participating in the database.

- Define the flow of patients referring to pain therapy centers to allow adequate health planning and the priority areas of intervention of the national health plan.

The data collected will facilitate the planning of future studies aimed to:

- define the impact of chronic pain at a local and national level, and its territorial and temporal variations over time, through prevalence and incidence measures;
- identify clinical subtypes, risk factors, predisposing and triggering factors;
- increase knowledge in the field of chronic pain to standardize diagnostic/therapeutic pathways and promote adequate management strategies.

2. Objectives

Primary Outcomes

Identify the profiles of patients belonging to pain therapy centers in terms of:

1. Location and type of pain
2. Prescribed therapies
3. Effectiveness of therapies
4. Time needed to reach the efficacy outcome

Secondary Outcome

1. Evaluate the proportion of patients who reach the outcome of 30 or 50% improvement
2. Evaluate the healthcare resources used in terms of number of visits and time needed to achieve the best outcome (30 or 50% improvement)
3. Identify patient profiles that are related to clinically significant outcomes and the specific treatments performed, plus their intermediate surrogate outcomes in relation to specific patterns

4. Describe the relevant clinical variables in the study population. In particular, the absolute and relative frequencies of those clinical variables relevant to the effectiveness of the treatment will be described, categorized by type of treatment, and the timing of the start of treatment with respect to the onset of pain. The data collected may be used for predictive analyses.

3. Study Design

This is a prospective, multicenter, non-profit observational cohort study. No intervention on patients outside of common clinical practice is envisaged.

The study is divided into three phases.

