5. PROCEDURES EXPECTED AND INFORMATION COLLECTED

Enrollment procedure

Adult patients of both sexes who belong to pain therapy centers with a diagnosis of Chronic Pain (pain that lasts > 12 weeks), regardless of the etiology, modality and age of onset, will be considered eligible for enrollment.

It will be possible to enroll patients during their first visit (FIRST ANESTHESIOLOGICAL VISIT), or during a check-up visit (ANESTHESIOLOGICAL CHECK-UP VISIT) or during a scheduled hospitalization for pain procedures (ORDINARY OR DAY HOSPITAL ADMISSION)

Patients will be asked to join the study after having been informed in detail (also with the aid of a written information form) of the objectives of the project, as well as the methods with which these objectives will be pursued. Participants will be informed about the lack of informative feedback regarding the results of future clinical evaluations: the results of any research originating from the register, in fact, will not be delivered to the participants themselves. The subject who freely accepts will authorize the inclusion of their data in the project by signing the informed consent form of which they will receive a copy. It will also be clearly explained in the information sheet attached to the informed consent that each participant will have the possibility of withdrawing their participation from the study at any time, without providing any reason and without this jeopardizing the doctor-patient relationship with the specialists involved in the project.

Patients will be informed by the manager of the patient's pain center or the principal investigator for the center (assuming this is not the same individual).

The doctor will complete the electronic CRF after evaluating the patient and classifying him according to the criteria of the IASP (International Association for the Study of Pain) in terms of primary or secondary chronic pain. In the case of a patient enrolled during a check-up or during hospitalization, all data relating to the time in which the patient is in care at the center, the

invasive procedures previously undertaken, the drugs prescribed, will be collected. Retrospective data (only for patients already being treated at the center) will be collected according to a predefined group (e.g.: the patient has been in the care of the center for: > 5 years; from 1 to 5 years; from 1 year to 6 months; from 3 to 6 months; < 3 months).

[figure not shown]
Follow-up procedure

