Once enrolled, the patient will be followed prospectively until the end of enrollment. At each visit it will be possible to retrieve the patient's chart and fill in the data relating to the intensity of pain and the treatments undertaken. It will also be possible to modify or add an etiological diagnosis in forms of secondary chronic pain. There is no limit to the number of follow-ups for each patient as long as the database is active (3 months from the date of enrollment of the last patient, considering a 12-month active enrollment expected for this study).

Data gathered

The activities of the registry do not replace routine diagnostic tests or visits to your doctor. The data collected by the registry will include relevant demographic data of the patient, comorbidities, the duration of the pain (> 5 years; from 1 to 5 years; from 1 year to 6 months; from 3 to 6 months), the type of pain, the location of the pain, the intensity of the pain (Brief Pain Inventory- Severity (BPI-S) and pain interference in daily activities (Brief Pain Inventory- Interference (BPI-I), treatments received (categorized according to pharmacological therapy, infiltrative therapy, ablative or neuromodulatory therapy, implants), the tests conducted, the number of other medical specialists contacted for the pathology being studied, the professional who sent it to the center. Specifically, the data collected is shown in Attachment 1
In particular, patients will be characterized by:

Type of pain (chronic primary or chronic secondary according to the scheme proposed by IASP)

Location of pain according to the following scheme (multiple options are possible)

- Lower back pain
- Thoracic
- Upper arts
- Lower limbs
- Head/Neck
- Pelvis

Pain Intensity

Brief Pain Inventory-Severity (BPI-S)

Interference with daily activities

Brief Pain Inventory-Interference (BPI-I)

Clinical information related to the pathology

Therapy
Pharmacological
Infiltrative
Implantable

Data collection methods and anonymization

The data collected will be used for scientific and epidemiological purposes. Each data will be created by a participating center and recorded on the SIAARTI Servers via a web application using the RedCap® data management software.

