6. ENDPOINT

Primary Endpoint

The number of patients referring to the centers, the type of pain, the proportion of patients who reach the clinically significant outcome, the type of therapies prescribed (pharmacological, neuromodulatory or implanted) necessary to achieve the outcome and the number of accesses and the Time in which a clinically significant improvement will be achieved (Change in BPI-s or BPI-I; a reduction of > 30% is considered clinically significant and a reduction of > 50% is considered optimal, the data will be evaluated for each Item).

Secondary Endpoint

1. The effectiveness of the treatments will be described in terms of
 - a. Change in pain intensity according to the Brief Pain Inventory-Severity questionnaire (BPI-S) A reduction of > 30% is considered clinically significant and optimal a reduction > of 50% the data will be evaluated for each Item)
 - b. b. Change in pain interference on daily activities according to the Brief Pain Inventory-Interference questionnaire (BPI-I). A reduction of > 30% is considered clinically significant and a reduction of > 50% is considered optimal; the data will be evaluated for each item)
2. Proportion of patients achieving clinically significant outcomes in relation to baseline characteristics and specific treatments performed and their intermediate surrogate outcomes in relation to specific patterns.
3. Resources used: Number of visits to the center for each patient in a year; Number of ordinary or day hospitalizations for each patient in a year.
4. The clinical variables relevant to the outcome will be described (e.g. type of pain, comorbidities, the time between treatment and clinically significant improvement, type of therapy undertaken - pharmacological, invasive, implant-based)

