12. ETHICAL CONSIDERATIONS

This observational study is designed and will be conducted according to the current protocol, in accordance with EU Directive 2001/20/EC relating to the implementation of the principles of good clinical practice in the conduct of clinical trials on medicinal products for human use, in accordance with the principles published in Good Clinical Practice (GCP) guidelines and in accordance with the Declaration of Helsinki on Ethical Principles for Medical Research Involving Human Subjects, adopted by the General Assembly of the World Medical Association (1996),

The investigator guarantees that personal patient data will be protected and processed in accordance with the General Data Protection Regulation (EU) 2016/679 (GDPR) on data protection and privacy.

ATTACHMENT 1

DATA GATHERED FOR EACH PATIENT

- ◇ CENTER CODE
- ◇ UNIQUE PATIENT CODE
- ◇ ACCESS METHOD (TO BE COMPLETED ONLY THE FIRST TIME FOR EACH PATIENT)
- ◇ DATE (the CRF must be filled in each time the patient has a visit/admission)
- ◇ SENT BY:
 - FAMILY DOCTOR
 - OTHER SPECIALIST
 - ADVICE FROM A RELATIVE/ACQUAINTANCE
 - WEB SEARCH
- ◇ REFERRAL METHOD (TO BE COMPLETED ONLY THE FIRST TIME FOR EACH PATIENT)
 - ◇ FIRST ANESTHESIOLOGICAL VISIT
 - ◇ ANESTHESIOLOGICAL CHECK-UP EXAMINATION
 - UNDER CARE AT THE CENTER FOR:
 - > 5 years;
 - from 1 to 5 years;
 - from 1 year to 6 months; or 3 to 6 months;
 - < 3 months
 - ◇ ORDINARY HOSPITALIZATION
 - IN EMPLOYMENT AT THE CENTER FOR:
 - > 5 years;
 - from 1 to 5 years;
 - from 1 year to 6 months; or 3 to 6 months;
 - < 3 months
 - ◇ DAY HOSPITALITY (DAY SURGERY OR DAY HOSPITAL)
 - IN EMPLOYMENT AT THE CENTER FOR:
 - > 5 years;
 - da 1 a 5 anni;
 - da 1 anno a 6 mesi; o da 3 a 6 mesi;
 - < 3 mesi

LEVEL 1: DEMOGRAPHICS

- ◇ AGE
- ◇ SEX
 - M
 - F

STATE/COUNTY OF RESIDENCE

SCHOOL LEVEL

- ◇ Not Known
- ◇ Grade School
- ◇ High School
- ◇ University

WORK

- ◇ WORKER
- ◇ UNEMPLOYED

COMORBIDITIES

- ◇ CARDIOVASCULAR
- ◇ DIABETES
- ◇ RESPIRATORY
- ◇ AUTOIMMUNITY
- ◇ CHRONIC INFLAMMATION
- ◇ OTHER

LEVEL 2: DIAGNOSIS

TYPE OF PAIN

- ◇ PRIMARY CHRONIC
 - CHRONIC WIDESPREAD PAIN
 - FIBROMYALGIA
 - OTHER
 - CRPS

- HEADACHE OR OROFACIAL PAIN
- MUSCULOSKELATAL
 - LOW-BACK PAIN
 - ALTRO
- ◇ SECONDARY CHRONIC
 - ONCOLOGICAL
 - POSTSURGICAL
 - LUMBAR
 - CERVICAL
 - BREAST
 - INGUINAL HERNIA
 - THORACOTOMY
 - OTHER
 - POST TRAUMATIC
 - CRPS
 - OTHER
 - NEUROPATHIC
 - PERIFERAL
 - POST-TRAUMATIC
 - DIABETIC
 - TRIGEMINAL
 - POST-HERPETIC

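### Attachment 1 lists CRPS under both primary and secondary chronic pain with no rule to separate the two boxes, so the primary/secondary split can depend on how a centre codes it

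*Protocol*

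**What the plan says.** Type of pain is a headline variable. The first item under Primary Outcomes in Section 2 is "Location and type of pain", and the primary endpoint in Section 6 begins with "The number of patients referring to the centers, the type of pain, the proportion of patients who reach the clinically significant outcome".

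Section 5 says how it is recorded. Under Enrollment procedure the doctor completes the electronic CRF after "classifying him according to the criteria of the IASP (International Association for the Study of Pain) in terms of primary or secondary chronic pain". Under Data gathered the item reads "Type of pain (chronic primary or chronic secondary according to the scheme proposed by IASP"). Several answers are expressly allowed for the next item: "Location of pain according to the following scheme (multiple options are possible"). Nothing comparable is said for type of pain. Under Follow-up procedure, "It will also be possible to modify or add an etiological diagnosis in forms of secondary chronic pain".

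Attachment 1, Level 2, Type of pain, gives the pick-list:

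- CRPS stands in the branch headed "PRIMARY CHRONIC", after chronic widespread pain and before headache/orofacial pain.
- CRPS stands again in the secondary branch, directly under the post-traumatic class.
- Trigeminal is an item under peripheral neuropathic pain and again under central neuropathic pain, both in the secondary branch.
- Post-traumatic is a secondary class of its own and also an item under peripheral neuropathic pain.
- Headache/orofacial pain and low-back pain each appear once in the primary and once in the secondary branch.

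Among the purposes of the database, Section 1 includes to "promote the use of uniform and comparable classification systems, definitions".

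**The concern.** A two-class variable needs classes that exclude each other. For CRPS the form offers the same diagnosis on both sides. The secondary box is limited to post-traumatic CRPS by its position, but the primary box carries no limit, so it also accepts CRPS after a fracture or other injury. Two centres seeing the same patient can each complete the form as written and place that patient in opposite classes.

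At stake are the frequency of primary and secondary pain, any description of response by type of pain, and comparison between centres. Section 8 also plans prevalence estimates for the pathologies with confidence intervals; those intervals express sampling error and do not cover differences in coding. Because Section 8 leaves detailed analysis plans to later protocols that draw on this database, those studies would inherit the ambiguity.

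**Working it through.** The Protocol states no figure on this point to reproduce. The check is a reading of the pick-list against the recording rule, followed by a bound.

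**Which overlaps can move the primary/secondary split**

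| Entity | First place | Second place | Can move the split? |
|---|---|---|---|
| CRPS | primary | secondary, post-traumatic | yes |
| Trigeminal | secondary, neuropathic peripheral | secondary, neuropathic central | no (0 points) |
| Post-traumatic | secondary, own class | secondary, neuropathic peripheral | no (0 points) |
| Headache/orofacial, low-back | primary | secondary | possibly intended: same entity, with or without an underlying cause |

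The branch headings alone place the two CRPS entries on opposite sides, so this does not depend on indentation that may have been lost from the list.

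**Bound for CRPS**

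Inputs: N = 2500 expected patients (Section 8, Sample Size). The CRPS share c is not given, so c = 1%, 2% and 5% are assumed. Let f be the fraction of CRPS patients entered in the primary box and p0 the share of all patients with other primary pain.

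Recorded primary proportion = p0 + c × f. As f runs from 0 to 1, it moves by c.

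| Assumed c | Patients affected, N × c | Maximum shift |
|---|---|---|
| 1% | 2500 × 0.01 = 25 | 1 point |
| 2% | 2500 × 0.02 = 50 | 2 points |
| 5% | 2500 × 0.05 = 125 | 5 points |

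For scale, the widest 95% half-width for a proportion at N = 2500, ignoring clustering by centre, is 1.96 × √(0.25/2500) = 1.96 × 0.01 = 0.0196, or 1.96 points. The worst-case coding shift is below this at c = 1%, about equal at 2%, and larger at 5%.

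This bound is for the split. A response proportion within a class would also move, by an amount that depends on how differently CRPS patients respond and on the size of the class. The Protocol gives neither, so I put no number on it.

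**The case against.** The strongest reply is that the branch is not a free choice. Section 5 tells the doctor to classify by IASP criteria first, and the box is then chosen within that branch. The double listing may also be deliberate, since headache/orofacial and low-back pain likewise appear in both branches. A figure following the enrolment procedure is not visible in the public text and might hold a decision scheme. Finally, the analysis is descriptive with exploratory tests, no primary-versus-secondary hypothesis is tested, and Phase 1 exists to settle the dataset.

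Part of this stands. Appearing in both branches is not in itself an error, and the consequence is for description and comparison, not for a formal test. The pointer to IASP does not settle CRPS, though: the form meant to apply that scheme offers both arms, and if it means post-traumatic versus other CRPS, the primary box does not say so. Phase 1 is the right time for the edit, but nothing in the Protocol schedules this particular one.

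A reader might go further in three ways that the Protocol does not support:

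- That the trigeminal and post-traumatic overlaps also distort the primary/secondary split. They lie wholly inside secondary pain.
- That the data could not be repaired. Both CRPS boxes name CRPS and can be pooled, and adding the two trigeminal boxes gives the trigeminal total. What stays uncertain is the peripheral/central division, and post-traumatic nerve pain filed under the residual item of the post-traumatic class, which cannot be identified later unless the centre amends it.
- That only one type may ever be recorded. The form is silent on several types at one visit, and secondary etiological diagnoses can be added or changed at follow-up.

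**Conclusion.** The point holds for CRPS. As printed, the pick-list lets the same CRPS patient be entered as primary or secondary, in a variable that belongs to the primary endpoint, and no visible rule decides. The effect on the primary/secondary split is at most the CRPS share: 1 to 5 points, or 25 to 125 of 2500 patients, if that share is 1% to 5%. The share is assumed, and the bound compares all CRPS coded one way with all coded the other; mixed practice across centres would give less in the pooled figure but would still disturb comparisons between centres.

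Separately and less seriously, the trigeminal and post-traumatic overlaps make some sub-class frequencies within secondary pain unreliable, without touching the split. Together these work against the stated aim of uniform classification; they do not invalidate the registry.

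**What to change.** In Attachment 1 and in REDCap, before Phase 2:

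1. List CRPS once, in the branch given by the IASP scheme that the Protocol cites, and recode or pool CRPS entries already made into that category.
2. Label the secondary post-traumatic class as non-neuropathic, so that post-traumatic nerve pain has a single box under peripheral neuropathic pain.
3. List trigeminal once, or label the central box so that the two entries exclude each other.
4. Leave headache/orofacial pain, low-back pain and similar entities in both branches where the primary/secondary distinction is intended. A blanket rule of one place per entity would wrongly merge them.

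The cost is a pick-list edit and a short recode, with no added burden on patients. Structuring the dataset is the stated task of Phase 1, so the change fits work already planned.

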6. ENDPOINT

Primary Endpoint

The number of patients referring to the centers, the type of pain, the proportion of patients who reach the clinically significant outcome, the type of therapies prescribed (pharmacological, neuromodulatory or implanted) necessary to achieve the outcome and the number of accesses and the Time in which a clinically significant improvement will be achieved (Change in BPI-s or BPI-I; a reduction of > 30% is considered clinically significant and a reduction of > 50% is considered optimal, the data will be evaluated for each Item).

Secondary Endpoint

1. The effectiveness of the treatments will be described in terms of
 - a. Change in pain intensity according to the Brief Pain Inventory-Severity questionnaire (BPI-S) A reduction of > 30% is considered clinically significant and optimal a reduction > of 50% the data will be evaluated for each Item)
 - b. b. Change in pain interference on daily activities according to the Brief Pain Inventory-Interference questionnaire (BPI-I). A reduction of > 30% is considered clinically significant and a reduction of > 50% is considered optimal; the data will be evaluated for each item)
2. Proportion of patients achieving clinically significant outcomes in relation to baseline characteristics and specific treatments performed and their intermediate surrogate outcomes in relation to specific patterns.
3. Resources used: Number of visits to the center for each patient in a year; Number of ordinary or day hospitalizations for each patient in a year.
4. The clinical variables relevant to the outcome will be described (e.g. type of pain, comorbidities, the time between treatment and clinically significant improvement, type of therapy undertaken - pharmacological, invasive, implant-based)

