4. STUDY POPULATION

The Registry data will be collected by the structures involved in the management of patients suffering from chronic pain, regardless of the cause. It is necessary to keep the inclusion criteria as broad as possible to obtain a real picture of clinical practice at a national level.

Inclusion criteria

- Subjects > 4 years old
- NRS > 4
- Diagnosis of Chronic Pain according to the IASP19 criteria
- Adherence through written informed consent to participate in the study

Exclusion criteria

- Patients suffering from psychiatric pathology or severe cognitive impairment for which the enrolling doctor does not believe it is useful for the purposes of the study
- Patients unable to sign the informed consent

Description of the pathologies being studied

Adult patients will be enrolled, diagnosed with Chronic Pain (pain lasting > 12 weeks), regardless of the etiology, modality, and age of onset.

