The study data will be collected and managed using the REDCap^{20,21} electronic data acquisition tools made available by SIAARTI. REDCap (Research Electronic Data Capture) is a secure, web-based software platform designed to support data capture for research studies. It provides:

- 1) an intuitive interface for acquiring validated data;
- 2) Controlled channels with customized access privileges for monitoring data manipulation and export procedures;
- 3) automated export procedures for continuous data download to common packages of statistical software;
- 4) procedures for data integration and interoperability with external sources.

Data will be recorded in the e-CRF only after being anonymized using coding procedures described in a separate document, in accordance with applicable data protection laws, including the EU GDPR. The encryption key of the anonymous data which contains the patient's name, surname and date of birth will be archived only in the files of the local site in a register that allows registration and research of the subject.

For each center participating in the project, an account will be created on the REDCap platform. The data will be recorded using an encrypted data connection (HTTPS) of anonymized input via a web browser or mobile app.

To enable data analysis, each patient will be assigned a unique Subject ID (Patient Identification Number).

REDCap is a secure web application for creating and managing online databases. Unauthorized access to data is impossible since access is permitted according to a hierarchical and role-based criterion. Access to REDCap will be allowed only to data collection personnel of the participating centers, according to the methods established by this protocol. These people will keep the information private.

Data management and storage

RedCap management software will be used for data management. The identification of individual patients by name will not be necessary or required at any time. During the collection and processing of data, therefore, all necessary measures will be adopted to effectively establish anonymization. SIAARTI will also take care of data storage. Each participating center can only access the patient data it has generated and registered on the REDCap platform. Each participating center is required to provide periodic ad hoc reports on the data collected.

Data ownership

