8. STATISTICAL ANALYSIS

All enrolled patients registered in the registry will be included in the analyses. A descriptive analysis will be performed on the collected data. In general, qualitative variables will be described using frequency distributions; the quantitative variables will be described by mean and standard deviation if normally distributed, and by median and interquartile range if asymmetrically distributed. As appropriate, statistical tests will be used for exploratory purposes. Treatment effects (Change in BPI-S and BPI-I scores) will be calculated as the ratio of the difference between baseline and follow-up scores to the baseline score. If the data allow it, inferential analysis will be applied on quantitative data (such as: comparison of Student's t means, Fisher's F, etc.), or on qualitative data (such as: chi square, odds ratio, Mann Whitney U, etc.). The prevalence of the different pathologies and the related confidence intervals will be estimated. Detailed statistical analysis plans will be set up in future research protocols that will use this database as a source of data.

Sample Size

Since this is an observational registry, no prior sample size calculation is required. Considering an expected participation of 12 centers, an estimate of 2500 patients included appears reasonable.

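### The first item of the primary endpoint asks for referral volume, but the registry can only count the patients it enrols

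*Protocol*

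**What the plan says.** The first item of the primary endpoint in Section 6 is "The number of patients referring to the centers". Among the purposes of the database, Section 1 lists: "Define the flow of patients referring to pain therapy centers to allow adequate health planning".

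Entry is governed by Section 4, which says of its own criteria: "It is necessary to keep the inclusion criteria as broad as possible to obtain a real picture of clinical practice at a national level". The list then requires age above 4 years, NRS above 4, an IASP diagnosis of chronic pain, and consent: "Adherence through written informed consent to participate in the study". It has two exclusions. One leaves room for judgement at the centre: "Patients suffering from psychiatric pathology or severe cognitive impairment for which the enrolling doctor does not believe it is useful". The other turns on the signature itself: "Patients unable to sign the informed consent".

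Attachment 1 sets out what is recorded, patient by patient. On centre reporting, Section 5 says: "Each participating center is required to provide periodic ad hoc reports on the data collected". Section 8 analyses every enrolled patient and adds: "The prevalence of the different pathologies and the related confidence intervals will be estimated". The same section expects 12 centres and about 2500 patients, without a sample size calculation.

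**The concern.** A count of patients who come to a pain centre needs a record of everyone who comes. This registry records only those who meet the pain threshold, are not excluded, are invited, and sign. A patient already controlled at NRS 4 or below, one who declines, or one who cannot sign leaves no trace. If the plan is followed as written, an enrolment count will be reported under the name of referral volume, in a project that wants the figure for planning services.

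Section 1 itself attributes poor pain networks partly to not knowing the influx to centres, and criticises existing data as incomplete or methodologically biased. A count with no denominator would repeat that weakness. No analysis plan could repair it, because numbers never collected cannot be recovered at the analysis stage.

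A smaller issue of the same kind sits in Section 8: the prevalence sentence names no denominator, so its confidence interval could be taken to apply to all patients who attend the centres.

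**Working it through.** **1. Endpoint against data.** I read referring to a centre as attending it, since Section 5 allows enrolment at first visits, check-ups and admissions.

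- *Wanted:* all patients attending (Section 6, first item; Section 1, purposes).
- *Admitted:* patients with NRS above 4, an IASP diagnosis and signed consent, and neither exclusion (Section 4).
- *Recorded:* individual items for admitted patients (Attachment 1). It holds no attendance total, screening count or refusal count, and the text of Section 5 mentions none. One figure in Section 5 is not shown in the copy reviewed.
- *Analysed:* enrolled patients (Section 8).

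The only obtainable count is the number enrolled. The protocol does not state that enrolment is consecutive.

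**2. Size of the gap.** The expected 2500 is a feasibility estimate with no formula behind it, so there is nothing to reproduce; 2500 / 12 = 208 per centre is arithmetic only. Let *c* be the fraction of attenders who are enrolled. Then attenders = enrolled / *c*. The documents give no *c*, so these values are assumptions:

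| Assumed *c* | Attenders behind 2500 enrolled |
|---|---|
| 0.9 | 2500 / 0.9 = 2778 |
| 0.7 | 2500 / 0.7 = 3571 |
| 0.5 | 2500 / 0.5 = 5000 |
| 0.3 | 2500 / 0.3 = 8333 |

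Nothing in Attachment 1 would tell these four situations apart.

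**3. The prevalence sentence.** Among enrolled patients a share *p* can be estimated well. The 95% half-width is 1.96 × √(*p*(1 − *p*)/2500):

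- *p* = 5%: 0.9 points
- *p* = 20%: 1.6 points
- *p* = 50%: 2.0 points

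Now suppose patients with a given pathology have *r* times the chance of enrolment of the others. The observed share is *pr* / (*pr* + 1 − *p*). With a true 20% share of attenders and an assumed *r* = 0.8, this is 0.16 / (0.16 + 0.80) = 16.7%. The half-width is 1.96 × √(0.167 × 0.833/2500) = 1.5 points, so the interval is 15.2% to 18.1%. With *r* = 1.25 the observed share is 0.25 / (0.25 + 0.80) = 23.8%, interval 22.1% to 25.5%. Both intervals are sound for enrolled patients, and both miss 20%. The interval covers sampling error only.

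**The case against.** The strongest reply is that the count is one item in a descriptive sentence. The primary outcomes in Section 2 are patient profiles: pain type and site, therapies, effectiveness, and time to benefit. None is a head count, and all can be computed among enrolled patients. Attachment 1 also records who sent the patient, the referral method, time under care and the date of each visit, so part of the flow is described. This stands, and it limits the point to total volume. It does not remove the mismatch, because Section 6 still names that volume as primary.

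A reader might infer that the prevalence in Section 8 cannot be measured at all. The documents do not support that. Section 8 takes all enrolled patients as its analysis set, so the relative frequency among them is estimable, and Section 1 leaves local and national prevalence to future studies. What is missing is the stated denominator.

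A reader might also infer that the periodic centre reports in Section 5 could supply the missing total. They are limited to data collected and are not said to be monthly. A breakdown into low NRS, excluded and declined would need a screening log of every attender. That would be a new collection; Attachment 1 has no separate NRS field even for enrolled patients, only BPI items.

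Nor do the documents show that enrolment practice differs between centres by any particular factor. That is possible, but no figure in the protocol bears on it.

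**Conclusion.** The point holds for the first primary item and the flow purpose: they name referral volume, and the data can yield only the number enrolled. The direction is known, since every filter removes attenders. The size is not: the range of 2778 to 8333 attenders for 2500 enrolled rests wholly on assumed capture of 90% to 30%. The other primary items are unaffected as descriptions of enrolled patients.

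For prevalence the conclusion is limited to wording. The estimate is valid among enrolled patients, and its interval says nothing about selection into the registry.

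This should be corrected in the protocol, because both remedies change either what the endpoint is called or what is collected.

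**What to change.** Choose one of two options for Section 6 and Section 1.

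1. *Rename.* Call the item the number of enrolled patients, and limit the flow purpose to describing referral routes and use of care among them. Cost: wording only.
2. *Keep flow as a goal.* Add one aggregate figure without patient data: the total number of patients seen per centre and period, over that centre's own enrolment window, because Section 3 has centres starting at different times. Count people, not visits, and report enrolled over seen beside it. Cost: a small new data item, to be written into Section 5 as such, since the existing centre reports do not contain it. It gives volume at the participating centres only. They join voluntarily and their final number is open, so it is not a national figure. The ratio also does not separate ineligibility, non-invitation and refusal.

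Under either option, add to Section 8 that the prevalence of pathologies is the relative frequency among enrolled patients, and that its confidence interval does not reflect selection into the registry. Cost: one sentence. No eligibility rule needs to change.
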